5.1. General Considerations

- ! The primary analysis will be performed after the database is locked and randomization schedule is released.
- ! The Control Period (CP), Treated Period (TP) and Maintenance Treatment Period (MP) are defined in [Table 5-1](#). Note, for participants randomized to the treatment group TP is period between initial treatment and maintenance treatment, which includes CP plus the follow-up period. For participants randomized to the control group TP is the follow-up period once the participants receive optional treatment. Follow-up Period (FP) starts on the end date of CP and ends on the same day as TP.

Table 5-1 Definition of the Control, Treatment and Maintenance Treatment Periods by Randomization Group

Randomization Group	Period	Treatment Group Label	Start Date	End Date
Treatment	CP	VOLUX	Initial treatment date	
The end date is the date of the Month 6 assessment:
 
 ! If multiple assessments fall into the Month 6 window, the date of the assessment included in the Month 6 analysis will be used as end date. ! For participants who exit before Month 6, the end date is study exit date. ! For participants with a missing assessment at Month 6, the end date is the target day for Month 6 (181 days from preceding treatment).
	TP	VOLUX	Initial treatment date	Date of maintenance treatment or the study exit date, whichever is earlier
	MP	VOLUX	Maintenance treatment date	Study exit date
Control	CP	Control	Randomization date	
For participants who do not receive optional treatment:
 
 ! If multiple assessments fall into the Month 6 window, the date of the assessment included in the Month 6 analysis will be used as end date. ! For participants who exit before Month 6, the end date is study exit date. ! For participants with missing assessment at Month 6, the target day for Month 6 (181 days from randomization date) will be the end date. ! For participants who receive optional treatment: the end date is the date of when the optional treatment is received.
	TP	VOLUX-Treated Control	Optional initial treatment date	Study exit date

- ! For CP, effectiveness analyses and baseline characteristics will be performed on the mITT population using the “as-randomized” assignment.
- ! For TP, effectiveness and safety summaries will be performed on the VT population using as-treated grouping.

- ! For MP, effectiveness and safety summaries will be performed on the VMT population.
- ! For applicable effectiveness and safety endpoints, baseline is defined as the last non-missing value on or before the latter of randomization date or first treatment date in the control period, unless otherwise specified.
- ! Descriptive statistics for continuous variables include the sample size (N), number of non-missing observations (n), mean, standard deviation, median, 1st and 3rd quartiles, minimum, and maximum. For continuous data, a 2-sample t-test or Wilcoxon rank test will be used for between group comparisons as appropriate, unless stated otherwise. Specified that 95% CI for continuous variables will be based on the standard normal distribution in Section 5.1.
- ! Summary statistics for categorical variables include the sample size (N1), frequency count, and percentage. Ordinal categorical variables will be analyzed using the Cochran-Mantel-Haenszel test. Nominal variables will be analyzed using Pearson's chi-squared test or Fisher's exact test as appropriate. The 95% CI will be computed using the exact binomial method.
- ! The level of significance used for all statistical tests will be 0.05, 2-sided, unless stated otherwise.
- ! The change from baseline values will be computed as the value for the post baseline visit minus the baseline value, unless otherwise indicated.
- ! In the event if any data collected was after exit, it will not be included in tables but will only be presented in the listings.
- ! All statistical analysis will be performed using SAS version 9.3 or higher.
- ! MedDRA 22.1 or newer will be used to code AEs and medical history.
- ! WHO Drug Dictionary 201703 or newer will be used to code medications.

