#### 8. Statistical Procedures

A separate statistical analysis plan will be prepared to provide specifications for all analyses. The plan will be finalized and approved prior to clinical database lock. One database lock is planned after all subjects exit the study.

Descriptive statistics will be presented for key outcome measures. Categorical variables will be summarized with frequency and relative frequency. Continuous variables will be summarized by number of subjects, mean, median, standard deviation, minimum, and maximum. Where appropriate, 2-sided 95% CIs for population mean, or population proportion, will be provided as part of the descriptive summary.

Every attempt will be made to collect complete data and limit the occurrence of missing data. Imputation of missing data may be used for sensitivity analysis of the primary effectiveness endpoint. Deviations from the analyses planned in the statistical plan will be documented in the clinical study report.

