3. Sample Size Determination

Sample size is determined to provide adequate power to demonstrate that the product is effective as well as safe. A sample size of 120 participants in the treatment group and 40 participants in the control group will provide > 99% power to detect a difference of at least 40% in the responder rates between the 2 groups. This calculation is based on a 1-sided Fisher's exact test at the 2.5% level. The treatment group is assumed to have at least an 80% responder rate and the control group is assumed to have at most a 40% responder rate. Assuming a screen fail rate of 25% and a drop-out rate of 15% between randomization and the Month 6 visit, up to 280 participants will be enrolled, with at least 144 participants and at most 162 participants randomized to the treatment group and at least 48 participants and at most 54 participants randomized to the control group (3:1 ratio).

This sample size is considered adequate to determine the safety profile of the product in the jawline area. Assuming a screen fail rate of 25%, a 5% drop-out rate between randomization and initial treatment for the treatment group, and a 15% drop-out rate between randomization and optional treatment for the control group, it is estimated that at least 176 subjects will be treated in the study. With 176 treated subjects, there is at least 92% power to detect an AE related to treatment with an incidence rate of 1.5% in the population using a 1-sided exact binomial test at the 2.5% level.

The commercial software, PASS (2008, Version 8.0.13), was used for the power calculation. The sample size calculation used an inequality test for 2 proportions to demonstrate that the treatment group is superior to the control group. The safety calculation used an inequality test for 1 proportion.

4. Populations for Analysis

The 5 analysis populations will consist of participants as defined in [Table 4-1](#).

Table 4-1 Analysis Populations

Population	Definition	Study Treatment Assignment
mITT	All randomized participants with non-missing baseline on the ALJDS scale on both sides of the jaw	As randomized
Observed Primary Endpoint	All mITT participants who have Month 6 assessment on the ALJDS scale on both sides of the jaw	As randomized
Safety	All randomized participants who receive study treatment (VOLUX or control)	As treated ^a

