5.4.2. Main Analytical Approach

For the secondary effectiveness endpoints of GAIS responder status at Month 6 as assessed by the EI and as assessed by the participant, the 95% CI will be provided for the proportion of responders within each treatment group, where applicable. These analyses will be performed on the mITT population.

No multiplicity adjustments will be made for the 2 GAIS responder rates since these endpoints are descriptive in nature.

For the secondary effectiveness endpoint of change from baseline in FACE-Q Satisfaction with Lower Face and Jawline overall score at Month 6 for the treatment group in the mITT population, a 2-sided paired t-test at the 5% level will be used to determine if the mean overall satisfaction score at Month 6 is statistically greater than that at baseline. This test will be

[figure not shown]
performed only if the co-primary endpoints are met. For items with missing data (which includes more than 1 response was selected, not applicable was selected, or a question was skipped), insert the mean of the completed items into the total sum score. If less than 50% of the questions have been answered (ie, number of missing items is 2 or more), then the overall score will be missing. The summary score including the imputation of missing items is rounded to the nearest integer and converted to the Rasch transformed score using the conversion table in Section 6.5.1.

Secondary effectiveness analyses are summarized in Table 5-5.

Table 5-5 Secondary Effectiveness Analyses

Endpoint	Description	Missing Data Handling Rule	Methodology
GAIS responder status as assessed by the EI at Month 6	Number (%) of responders by treatment group	Observed data is used; no imputation is needed	Categorical descriptive statistics
GAIS responder status as assessed by the participant at Month 6	Number (%) of responders by treatment group	Observed data is used; no imputation is needed	Categorical descriptive statistics
Mean change from baseline in Rasch transformed score of FACE-Q satisfaction with lower face and jawline at Month 6	Mean change from baseline within the treatment group	No imputation. Only observed data will be used in the analysis.	2-sided paired t-test

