6.2.2. SAP Version History

The following are the changes to version 2 of SAP:

1. Updated the criteria for receiving touch-up treatment based on the protocol in Section 1.2.
2. Updated the number of imputed datasets used for the primary effectiveness endpoint analysis from 5 to 30 datasets in Sections 2 and 5.3.2 to reduce variability and increase efficiency of estimates. Changed the seed in Step 1 to keep it consistent with what was used in the lines of SAS code. Added the “likelihood=augment” option in the PROC MI SAS code in case the data has either complete separation pattern or quasi-complete separation pattern.
3. The naming of the analysis population for the sensitivity analysis of primary endpoint, ALJDS responder status at Month 6 was changed from “Completer Population” to “Observed Primary Endpoint” in Sections 4, 5.3.3, and 6.2.1. The definition of this population refers to the completion of the primary timepoint visit (ie., Month 6 of CP). This naming change is aimed to avoid potential confusion with study completion.
4. Updated the definition of TP for the control group to “follow-up period once the participants receive the optional treatment” and starts in the end date of CP in Section 5.1.
5. The definition of “baseline” for the effectiveness and safety variables in Sections 5.1 and 6.2.1 was changed to “the last non-missing assessment prior to the latter of randomization or first treatment in the control period” due to possibility of participants who were mistreated (ie., either randomized to VOLUX but was not treated or randomized to Control but received VOLUX).
6. Specified that 95% CI for continuous variables will be based on the standard normal distribution in Section 5.1.
7. Added that the exact binomial method will be used to compute 95% CI for categorical variables in Section 5.1.
8. Added a bullet regarding how if any data is collected after exit then it will be summarized in the tables and listings in Section 5.1.
9. The wording of “Rasch transformed score” were specified for the analyses of FACE-Q Satisfaction with Lower Face and Jawline and FACE-Q Appraisal Lines: Marionette in Sections 5.4.1, 5.4.2, and 5.5 and to enhance clarity and consistency with Appendix 6.5.
10. The definition of change from baseline was moved from Section 5.4.1 to Section 5.1

11. Added clarification in Section 5.4.2 that analyses will be performed on the mITT population.

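### SAP 5.1 builds 95% CIs for means from the normal distribution although the SD is estimated; any such interval is slightly too narrow, by about 1% to 3% at the group sizes the documents support

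*SAP*

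**What the plan says.** SAP 5.1 (General Considerations), in the bullet on continuous variables, says that "95% CI for continuous variables will be based on the standard normal distribution". The rule is deliberate: SAP 6.2.2 lists it as item 6 of the version 2 changes, "Specified that 95% CI for continuous variables will be based on the standard normal distribution in Section 5.1". The sentence in 5.1 has that same wording, including the reference to its own section, so a change-log entry now stands in the operative text.

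The same 5.1 bullet names a 2-sample t-test (or a Wilcoxon test) for comparing groups on continuous data. For the FACE-Q change at Month 6 in the treatment group, SAP 5.4.2 says that "a 2-sided paired t-test at the 5% level will be used", and Table 5-5 adds "No imputation. Only observed data will be used in the analysis".

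Intervals for means come into the plan through Protocol Section 8: "Where appropriate, 2-sided 95% CIs for population mean, or population proportion, will be provided as part of the descriptive summary". The protocol names no distribution for them.

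**The concern.** A normal-based interval for a mean has exact coverage for normal data only when the SD is known. Here it is estimated each time, so mean ± 1.96 standard errors covers less than 95%, and the shortfall grows as the group gets smaller. The error always goes one way, towards overstated precision.

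The rule also sits badly with the rest of the SAP. Means are tested with t-tests but would be given intervals that do not invert those tests. Proportions, in the next bullet of 5.1, get exact binomial intervals. What is at stake is the nominal coverage of descriptive intervals, mainly in groups smaller than the treatment arm.

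**Working it through.** **Inputs**

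- Critical value under SAP 5.1: z = 1.960.
- Planned evaluable numbers, SAP Section 3: "A sample size of 120 participants in the treatment group and 40 participants in the control group will provide > 99% power".
- Randomized: 144 to 162 treatment and 48 to 54 control, with 15% drop-out to Month 6. SAP Section 3 also applies 15% to controls between randomization and optional treatment.
- Evaluable treatment group: 144 × 0.85 = 122.4 and 162 × 0.85 = 137.7, so about 122 to 138. The planned minimum of 120 is included as well.
- Treated controls: 48 × 0.85 = 40.8 and 54 × 0.85 = 45.9, so about 41 to 46. This assumes that every control who remains accepts treatment.
- Touch-up and maintenance: no counts in the documents. n = 20 is an assumption, for illustration only.

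**The plan's own figures.** The documents state no interval width or coverage, so there is nothing to reproduce on this point directly. The sample-size statement that supplies the group sizes does reproduce: 120 versus 40, 80% versus 40% responders, 1-sided Fisher's exact test at 2.5%, gives exact power of 99.4% against the stated figure of more than 99%.

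**Formulas** (normal data, within-group mean)

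- Relative shortfall in width = 1 − 1.960 / t(0.975, n−1)
- True coverage of mean ± 1.960 SE = 2 × F(1.960; n−1) − 1, where F is the t distribution function with n−1 degrees of freedom

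**Results**

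| n | Group | t(0.975, n−1) | z interval too narrow by | Coverage |
|---|---|---|---|---|
| 120 | treatment, planned minimum | 1.980 | 1.02% | 94.77% |
| 122 | treatment, 144 less 15% | 1.980 | 1.00% | 94.77% |
| 138 | treatment, 162 less 15% | 1.977 | 0.88% | 94.80% |
| 46 | treated controls, 54 less 15% | 2.014 | 2.69% | 94.38% |
| 41 | treated controls, 48 less 15% | 2.021 | 3.02% | 94.30% |
| 20 | assumption only | 2.093 | 6.36% | 93.52% |

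Example, n = 41: 1.960 / 2.0211 = 0.9698, so the interval is 3.02% too narrow.

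**Could a FACE-Q interval contradict the FACE-Q test?** At n = 120, a normal-based interval would exclude zero while the paired t-test is non-significant only if |t| lies between 1.960 and 1.980, that is, p between 0.0500 and 0.0523. The chance of that is about 0.2% if there is no true change and at most 0.8% under the least favourable true change.

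**The case against.** The strongest reply is that little in the visible plan is affected.

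- The list of descriptive statistics for continuous variables in SAP 5.1 contains no interval. The visible touch-up and maintenance summaries of volume, anesthesia duration and pain are plain descriptive statistics. This stands: apart from the general statement in Protocol Section 8, no visible text plans an interval for a particular mean. SAP 5.5 on other effectiveness endpoints is not visible, so intervals there can be neither assumed nor ruled out.
- Very small groups are not documented. The one in-document guide is Protocol 2.2, where the previous study had 119 participants after initial or touch-up treatment and 89 after repeat treatment. It is a different study, but at n = 89 the interval would be only 1.4% too narrow, with 94.7% coverage. This stands, and n = 20 is therefore only an illustration.
- A large-sample normal interval is a common convention, and the t interval is itself only approximate for a bounded score such as FACE-Q. This is fair. It makes the gap small in the treatment arm, but it gives no reason to prefer the normal rule.

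A reader might go further and infer that the FACE-Q result could be contradicted by its own confidence interval. The documents do not support that. SAP 5.4.2, Table 5-5 and Protocol 8.3.2 give FACE-Q a paired t-test and name no interval, the decision rests on the test, and disagreement would need a p-value in a very thin band just above 0.05.

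**Conclusion.** The point holds as a minor one. The rule in SAP 5.1 does not match an estimated SD or the SAP's own t-tests, and any interval built on it is slightly too narrow: about 1% in the treatment group and about 3% for treated controls, with coverage of 94.8% and 94.3% to 94.4% instead of 95%. These figures assume normal data and the drop-out rates stated in SAP Section 3. Lower uptake of optional treatment, or further loss afterwards, would make the treated-control group smaller and the shortfall somewhat larger.

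No conclusion of the trial is at risk. The primary endpoint is a proportion with its own pooled interval under SAP 5.3.2, the GAIS endpoints are proportions, and the FACE-Q test already uses the t distribution. Sample size and power are unaffected.

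**What to change.** Replace the pasted change-log sentence in SAP 5.1 with: *95% CIs for means and mean changes will use the t distribution (n−1 degrees of freedom for within-group means).*

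This aligns within-group intervals with the paired t-test, gives nominal coverage at every group size under normality, and removes the stray wording. It costs one sentence and an entry in the SAP change list. Intervals become wider by about 1% in the treatment group (1.980 / 1.960 = 1.010 at n = 120) and about 3% for treated controls (2.021 / 1.960 = 1.031 at n = 41).

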5.2. Participant Dispositions

The number of participants in each of the 4 study populations (mITT, Safety, VT, and VMT) will be summarized by treatment group.

The number of participants screened will be summarized. Screen-failure participants (ie, participants who are screened but are not randomized) and the associated reasons for failure as recorded in the eCRF will be listed for the all screened participants.

CONFIDENTIAL

JUVÉDERM VOLUX™ XC

Statistical Analysis Plan V25L-002

Study disposition will be summarized for all screened participants overall and by treatment group for the following:

- ! Number of participants screened (overall)
- ! Number of participants randomized; this number will be used as the denominator to compute the following percentages
 - o Number of participants treated as randomized
 - o Number of participants treated not as randomized

For mITT Population during CP

- ! Number of participants completed CP
- ! Number of participants discontinued during CP
- ! Reasons for discontinuation during CP

For VT Population after CP

- ! Number of participants who continued after CP
- ! Number of participants who completed FP
- ! Number of participants who discontinued during FP
- ! Reasons for discontinuation during FP

For VMT population during MP

- ! Number of participants who received maintenance treatment
- ! Number of participants who completed MP
- ! Number of participants who discontinued during MP
- ! Reasons for discontinuation during MP

For mITT Population during the study

- ! Number of participants who completed the study
- ! Number of participants who discontinued from the study
- ! Reasons for discontinuation from the study

A participant is considered to have completed the study if he/she has completed the study exit visit. Treatment group participants who elect not to receive maintenance treatment are considered completers if they complete the Month 12 visit. Control group participants who do not elect to receive optional treatment are considered completers if they complete the Month 6 visit. The end of the study is defined as the date of the last visit of the last participant in the study.

5.3. Primary Effectiveness Endpoint Analysis

5.3.1. Definition of Endpoint

The primary effectiveness endpoint is the ALJDS responder status at Month 6 in CP based on EI's assessment. A responder is defined as a participant who achieves at least 1-point improvement (reduction) from baseline on the photonumeric ALJDS (described in [Table 5-2](#)) on both sides of the jaw.

Table 5-2 Allergan Loss of Jawline Definition Scale

Score	Grade	Description
0	None	
1	Mild	
2	Moderate	
3	Severe	
4	Extreme	

5.3.2. Main Analytical Approach

Two hypotheses regarding the proportion of ALJDS responders at Month 6 based on EI's assessment will be tested.

$$1) H_0: P_v < 50\%$$

$$H_a: P_v \geq 50\%$$

$$2) H_0: P_v \leq P_c$$

$$H_a: P_v > P_c$$

P_v denotes the responder rate for the treatment group at Month 6 after the preceding treatment and P_c denotes the responder rate for the control group at Month 6 after randomization.

The 2 hypotheses will be tested using the multiple imputation method as follows:

Step 1: The missing data will be imputed by each side of the jaw and treatment group using the fully conditional specification method with seed = 3575309 and nimpute = 30 based on the following model:

$$\text{Month 6 ALJDS} = \beta_0 + \beta_1 \text{Baseline ALJDS} + \beta_2 \text{Month 1 ALJDS} + \beta_3 \text{Month 3 ALJDS}$$

Step 2: After imputation, the changes from baseline will be calculated, from which the responder status in ALJDS at Month 6 of CP will be determined.

Step 3: Each complete dataset obtained from Steps 1 and 2 will be analyzed using SAS procedure FREQ

Step 4: The pooled results will be obtained using PROC MIANALYZE using normal approximation

The number and proportion of participants who achieved at least 1-point improvement from baseline at Month 6 during CP will be tabulated by treatment group. The pooled responder rates by treatment group and the associated p-value and 95% CI estimates based on the normal approximation will be presented. For the first hypothesis, the null hypothesis will be rejected if the lower bound of the 95% CI on the responder rate at Month 6 for VOLUX is greater than or equal to 50%. For the second hypothesis, if the 2-sided p-value is less than 0.05, then the ALJDS responder rate at Month 6 in JUVÉDERM VOLUX XC is statistically significantly different

[figure not shown]
CONFIDENTIAL

[figure not shown]
JUVÉDERM VOLUX™ XC

Statistical Analysis Plan V25L-002

from that in the no-treatment control group during the control period. Furthermore, if the responder rate is greater for JUVÉDERM VOLUX XC than the no-treatment control group, then VOLUX will be considered superior to the no-treatment control group.

The detailed SAS codes are as follows:

